8.4.3 General Data Analysis

The summary of the demographic characteristics will be presented. Continuous variables will be summarized using mean (SD) or median (interquartile range) depending on whether or not the data follow the normal distribution. Categorical variables will be summarized by frequency (percentage). All adverse events will be presented as listings. All analysis will be performed using SAS version 9.4 (SAS Institute Inc. Cary, NC, USA).

8.5 Withdrawal of Patients

Patients may withdraw from the study treatment and assessments at any time. Specific reasons for withdrawal include:

- A. Voluntary withdrawal of consent by the patient or guardian
- B. Safety reasons requiring discontinuation as determined by the physician(s) caring for the patient
- C. Non-compliance to protocol
- D. Loss to follow-up
- E. Completion of all study procedures and follow-up

8.6 Stopping Rules

Phase Ib Stopping Rules

If 3 of 7 patients in a single cohort experience a treatment-related limiting toxicity (after combined checkpoint inhibitor treatment is initiated) defined as a ≥ grade 4 non-hematologic toxicity as specified by the Common Terminology Criteria for Adverse Events v4.03 (CTCAE), that single cohort will be terminated. Exceptions listed in section 5.9 apply to this endpoint as well. (http://ctep.cancer.gov/reporting/ctc.html)

Phase IIA Stopping Rules

Toxicity monitoring rule for each cohort of 37 patients treated with ipilimumab/nivolumab in Phase IIA was derived using toxicity based on repeated significance testing method obtained from R-Package "Clinfun" in R version 3.4.3, the R Foundation for Statistical Computing, Vienna, Austria. Based on toxicity rate observed in Phase 1b, we considered toxicity rate of 0.25 to be the acceptable rate and occurrence rate of 0.30 to the unacceptable rate of toxicity. Thus, using CLINFUN function 'toxbdry' with arguments pLo=0.25, pHi=0.30, sequence of looks 2:37, significance level (probability of declaring treatment as unacceptable when toxicity rate is 0.30=0.10, 90% power of declaring Ipinivo treatment with toxicity 0.30 as unacceptable, boundary shape parameter delta=0.15 and taking the alternative priority error threshold, the monitoring rule given in Table 7 was obtained.

Table-A Stopping Boundaries for combined checkpoint inhibition with nivolumab and ipilimumab after autologous hematopoietic stem cell transplantation						
	Number of Patients at	Stop if Number of Toxicities is				
Monitoring Look	Monitoring Look	at least				
1	2	1				
2	5	2				
3	9	3				
4	13	4				
5	17	5				
6	21	6				
7	25	7				
8	29	8				
9	33	9				
10	37	10				

In each expansion cohort of size 37 the trial will be terminated based on the above table-A using the rules:

Out of the first 2 patients, stop if 1 or more report toxicities. Out of the first 5 patients, stop if 2 or more report toxicities. Out of the first 5 patients, stop if 2 or more report toxicities. Out of the first 9 patients, stop if 3 or more report toxicities. Out of the first 13 patients, stop if 4 or more report toxicities. Out of the first 17 patients, stop if 5 or more report toxicities. Out of the first 21 patients, stop if 6 or more report toxicities. Out of the first 25 patients, stop if 7 or more report toxicities. Out of the first 29 patients, stop if 8 or more report toxicities. Out of the first 33 patients, stop if 9 or more report toxicities. Out of the first 37 patients, stop if 10 or more report toxicities.

Table-B Operating Characteristics of Toxicity Monitoring for Pa=0.25 vs Pu=0.30 (n=37)								
	Expected Expected							
	Prob. of Prob. of Sample Prob. of Prob. of Sample							
Toxicity		crossing	stopping	size for	crossing	stopping	size for	
rate	Toxicity	low	low	low	high	high	high	
number	Rate	boundary	boundary	boundary	boundary	boundary	boundary	

1	0.25	0.781	0.776	13.3	0.772	0.766	13.9
2	0.26	0.810	0.805	12.5	0.802	0.796	13.0
3	0.27	0.837	0.831	11.7	0.830	0.824	12.2
4	0.28	0.861	0.856	10.9	0.855	0.849	11.4
5	0.29	0.883	0.877	10.2	0.877	0.872	10.6
6	0.30	0.902	0.897	9.5	0.897	0.892	9.9
P _a , toxicity	rate that is a	cceptable; F	o _{u.} toxicity ra	te that is una	acceptable; F	Prob, probab	oility

From the operating characteristics in Table B, it observed that the stopping guideline will have 90% power (prob. crossing high boundary=0.897) to terminate the trial in any cohort of size 37 when the true toxicity rate is 0.30, and expected sample size for early termination at this rate will be 10 patients(expected sample size for high boundary=9.9).

The definition of unacceptable toxicity will be as follows:

- Any Grade 2 drug-related uveitis or eye pain or blurred vision that does not respond to topical therapy and does not improve to Grade 1 severity within the re-treatment period OR requires systemic treatment
- Any Grade 3 non-skin, drug-related adverse event lasting > 7 days, with the following exceptions for drug-related laboratory abnormalities, uveitis, pneumonitis, bronchospasm, diarrhea, colitis, neurologic adverse event, hypersensitivity reactions, and infusion reactions
 - Grade 3 drug-related uveitis, pneumonitis, bronchospasm, diarrhea, colitis, neurologic adverse event, hypersensitivity reaction, or infusion reaction of any duration requires discontinuation
 - Grade 3 drug-related laboratory abnormalities do not require treatment discontinuation except those noted below
 - Grade 3 drug-related thrombocytopenia > 7 days or associated with bleeding requires discontinuation
 - Any drug-related liver function test (LFT) abnormality that meets the following criteria require discontinuation:
 - AST or ALT > 8 x ULN
 - Total bilirubin > 5 x ULN
 - Concurrent AST or ALT > 3 x ULN and total bilirubin > 2 x ULN
- Any Grade 4 drug-related adverse event or non-hematological laboratory abnormality, except for the following events which do not require discontinuation:
 - Isolated Grade 4 amylase or lipase abnormalities that are not associated with symptoms or clinical manifestations of pancreatitis and decrease to < Grade 4 within 1 week of onset.
 - Isolated Grade 4 electrolyte imbalances/abnormalities that are not associated with clinical sequelae and are corrected with supplementation/appropriate management within 72 hours of their onset
- Any Grade 5 drug-related death

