
	collected within 48 hours prior to transplant admission), at engraftment (within 72 hours of ANC ≥ 500), and then serially, on day 1 of week 1 (to be collected within 48 hours prior to clinic visit) and then weeks 4, 7, 12, 18, and 26, End of Treatment and 9, 12, 15 and 18 months post-transplant, and at time of relapse, as it occurs.
Phase IIA	The primary objectives of this study are:
Primary Objective	 To assess progression-free survival at 18 months after ASCT in patients in cohorts that were deemed safe in Phase Ib (no more than 3 treatment- related toxicity) and at least 4 of 7 patients were progression free at 18 months in the Phase Ib.
Phase IIA	The secondary objectives of this study are:
Secondary Objectives	 To assess complete response rate at 3, 6 and 12 months after ASCT in patients at high risk for post-transplant recurrence including patients in the successor expansion cohorts following the Phase Ib trial. To assess progression-free survival at 12 months after ASCT in patients at high risk for post-transplant recurrence including patients with in the successor expansion cohorts following the Phase Ib trial. Determine the toxicities resulting from administration of the treatments in patients enrolled in the successor expansion cohorts following the Phase Ib trial. To assess blood immune reconstitution, phenotype and TCR repertoire at screening (at time of informed consent), at apheresis (stem cell collection), and then serially the day 1 of week 1 of combined checkpoint inhibitors and then weeks 4, 7, 12, 18 and 26, End of Treatment, and at 9, 12, 15, and 18 months post-transplant and at time of relapse, as it occurs.
Phase IIA Tertiary Objectives	• To identify specific intestinal microbial strains associated with improved outcome in autologous stem cell transplantation patients treated with combined checkpoint inhibitors. The overall microbial composition in stool samples of patients will be analyzed at screening, preconditioning (to be collected within 48 hours prior to transplant admission), at engraftment (within 72 hours of ANC ≥ 500), and then serially, on day 1 of week 1 (to be collected within 48 hours prior to clinic visit) and then weeks 4, 7, 12, 18, and 26, End of Treatment and 9, 12, 15 and 18 months post-transplant, and at time of relapse, as it occurs.

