1.0 OBJECTIVES

This is an open label, single-arm per cohort, phase Ib-IIA study.

Our goal is to determine the safety and clinical effect of combined checkpoint inhibition administered after autologous hematopoietic stem cell transplantation in each of six clinical cohorts of high risk and recurrent disease. In addition to assessing the incidence and severity of adverse events and rates of complete response and progression free survival, we intend to monitor immune reconstitution, phenotype and TCR repertoire throughout treatment and at the time of disease progression. We will also analyze the gut microbiome prior to conditioning, throughout treatment, post-transplant and at time of relapse. We intend to expand cohorts in the lymphoma groups that demonstrate safety and PFS >50% at 18 months into a phase IIA successor trial.

Phase Ib

The primary objectives of this study are:

 To assess the safety of combined check point inhibition with nivolumab and ipilimumab after autologous hematopoietic stem cell transplantation in patients at high risk for post-transplant recurrence including patients with persistent and recurrent high risk diffuse large B cell lymphoma, high risk and recurrent T cell lymphoma and high risk and recurrent multiple myeloma.

Primary endpoints:

- Safety endpoint: The composite endpoint consisting of the occurrence of at least one treatment-related limiting toxicity (after combined checkpoint inhibitor treatment is initiated) defined as a ≥ grade 4 non-hematologic toxicity as specified by the CTCAE. Exceptions listed in section 5.9 apply to this endpoint as well. If 3 of 7 patients in a single cohort experience a treatment-related limiting toxicity, that single cohort will be terminated.
- Efficacy endpoint: progression-free survival at 18 months after ASCT in patients at high risk for post-transplant recurrence including patients with persistent and recurrent high risk diffuse large B cell lymphoma, high risk and recurrent T cell lymphoma and high risk and recurrent multiple myeloma.

The secondary objectives are:

- To assess complete response rate at 3, 6 and 12 months after ASCT in patients at high risk for post-transplant recurrence including patients with persistent and recurrent high risk diffuse large B cell lymphoma, high risk and recurrent T cell lymphoma and high risk and recurrent multiple myeloma.

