- To assess tumor site immune phenotype, T cell repertoire and PD L1/2 expression when tissue available for biopsy prior to autologous transplant conditioning and

then at time of progression (within 18 months) after autologous transplant conditioning.

The tertiary objectives are:

• To identify specific intestinal microbial strains associated with improved outcome in autologous stem cell transplantation patients treated with combined checkpoint inhibitors. The overall microbial composition in stool samples of patients will be analyzed at screening, preconditioning (to be collected within 48 hours prior to transplant admission), at engraftment (within 72 hours of ANC ≥ 500), and then serially, on day 1 of week 1 (to be collected within 48 hours prior to clinic visit) and then weeks 4, 7, 12, 18, and 26, End of Treatment and 9, 12, 15 and 18 months post-transplant, and at time of relapse, as it occurs. A 16S ribosomal RNA (rRNA) miSeq Illumina platform will be used for overall microbial composition and quantitative real-time PCR analysis will validate the specific microbial strains identified by miSeq.

Phase IIA

The primary objectives of this study are:

• To assess progression-free survival at 18 months after ASCT in patients in cohorts that were deemed safe in Phase Ib (no more than 3 treatment-related toxicity) and at least 4 of 7 patients progression free at 18 months in the Phase Ib.

The secondary objectives of this study are:

- To assess complete response rate at 3, 6 and 12 months after ASCT in patients at high risk for post-transplant recurrence including patients in the successor expansion cohorts following the Phase Ib trial.
- To assess progression-free survival at 12 months after ASCT in patients at high risk for post-transplant recurrence including patients with in the successor expansion cohorts following the Phase Ib trial.
- Determine the toxicities resulting from administration of the treatments in patients enrolled in the successor expansion cohorts following the Phase Ib trial.
- To assess blood immune reconstitution, phenotype and TCR repertoire at screening (at time of informed consent), at apheresis (stem cell collection), and then serially the day 1 of week 1 of combined checkpoint inhibitors and then weeks 4, 7, 12, 18 and 26, End of Treatment, and at 9, 12, 15, and 18 months post-transplant and at time of relapse, as it occurs.

The tertiary objectives are:

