8.1 Determination of Sample Size

- The Phase Ib feasibility trial will require 42 patients divided in 6 cohorts, with 7 patients each. Enrolled patients will have hematologic malignancies with a high risk for post-autologous stem cell transplant recurrence including patients with persistent and recurrent high risk diffuse large B cell lymphoma, high risk and recurrent T cell lymphoma and high risk and recurrent multiple myeloma.
- The Phase IIA will require up to 148 patients, assuming all cohorts followed in Phase Ib meet the criteria for expansion.

Accrual goal is 7 patients per cohort. Accrual period goal is 36 months. Patients will accrue to study by disease groups (cohorts) and followed separately by group for incidence and severity of toxicity, ability to receive intended schedule of combined checkpoint inhibitors and for complete response and progression free survival (PFS) rates. Complete response and progression free survival rates will be compared to published standards for each disease group. Expected PFS at 18 months (PFS18) for all post-transplant groups without checkpoint inhibitors is 40-50%¹⁻³. Groups A, B, C, and D with PFS at 18 months in 4 or more patients (57%) will be considered for eligibility in a successor phase IIa expansion trial. The primary efficacy endpoint of the phase Ib portionis to achieve PFS of 18 months in ≥4 patients per cohort (≥57%).

Phase Ib

The initial part of the trial titled is designed as a feasibility Phase Ib study. This will determine which of 6 cohorts of patients would be studied in an expansion Phase IIa trial. In this pilot feasibility study, designed to assess the safety of the combined checkpoint inhibitor, sample size was not performed to estimate power, as it was designed to obtain initial estimates of toxicity to inform the successor trial Phase IIA. Therefore, this pilot feasibility study is not powered to detect significant differences in PFS. We have preemptively established a cut-off of ≥57% PFS at 18 months as the minimum benefit needed to proceed to Phase IIa for each individual cohort, if a maximum of 3 patients in each cohort experience severe adverse events which would lead to trial discontinuation (for that particular cohort). Historical data for such patient populations predicts PFS 40-50% at 18 months.

Phase IIa

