8.3 Statistical Methods

8.3.1 Safety Analysis

The safety of combined checkpoint inhibition with nivolumab and ipilimumab, after autologous hematopoietic stem cell transplantation in patients at high risk for post-transplant recurrence, will be evaluated for composite endpoint (at least one treatment-related toxicity and all adverse events observed in each cohort and presented as counts (percentages) and corresponding exact binomial 95% confidence intervals for proportion. Adverse events will include Immune-mediated colitis, hepatitis, endocrinopathies, nephritis, rash, encephalitis and immune-related AEs (irAEs).

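### At exactly 3 of 7 toxicities, the Phase Ib stopping rule ends the cohort while the Phase IIA entry rule calls it safe

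*Combined protocol and SAP*

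**What the plan says.** **Termination.** Section 8.6 gives the Phase Ib stopping trigger as "If 3 of 7 patients in a single cohort experience a treatment-related limiting toxicity", with termination of that cohort as the consequence. Section 1.0 (Phase Ib primary endpoints) states: "If 3 of 7 patients in a single cohort experience a treatment-related limiting toxicity, that single cohort will be terminated". The synopsis and section 8.0 repeat the rule. The event is defined as a treatment-related non-hematologic toxicity of CTCAE grade 4 or higher after checkpoint inhibition starts, subject to the exceptions in section 5.9.

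**Entry to Phase IIA.** The synopsis restricts the Phase IIA primary objective to "cohorts that were deemed safe in Phase Ib (no more than 3" treatment-related toxicities. Sections 1.0 and 8.0 have the same limit: "deemed safe in Phase Ib (no more than 3 treatment-related toxicity". All three add a second condition, that at least 4 of 7 patients are progression free at 18 months.

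**Sample size.** Section 8.1 lets a cohort that meets the PFS cut-off proceed "if a maximum of 3 patients in each cohort experience severe adverse events which would lead to trial discontinuation (for that particular cohort". It also says that lymphoma groups meeting the PFS criterion "will be considered for eligibility in a successor phase IIa expansion trial".

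**Related wording.** Section 8.3.1 describes the safety endpoint as "composite endpoint (at least one treatment-related toxicity", without the qualifier that makes a toxicity limiting. For Phase IIA, section 8.6 states: "we considered toxicity rate of 0.25 to be the acceptable rate and occurrence rate of 0.30 to the unacceptable rate of toxicity".

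**The concern.** Three is a count that triggers termination and also a count that is no more than three. The two rules agree everywhere except at this value, which is where the decision turns.

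The decision is the primary safety conclusion of Phase Ib and the gate to Phase IIA. On the lenient reading, a cohort with an observed rate of 3/7 = 43% would enter a phase that treats 30% as unacceptable. The Phase IIA toxicity definition is also broader: it largely contains the Phase Ib event and adds certain grade 2 and grade 3 events. A 43% rate on the narrower event is therefore not explained away by the change of definition.

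The terms differ as well. The entry rule refers to treatment-related toxicity and section 8.1 to severe adverse events. Both are probably shorthand for the limiting toxicity, but neither is the defined term. The entry rule does not say whether it counts patients or events.

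Section 8.6 says the Phase IIA rates were based on toxicity seen in Phase Ib, so some Phase Ib results were known when that text was written. An unresolved threshold then leaves room for a choice made after seeing the count.

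**Working it through.** **1. The rules side by side**

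| Patients with limiting toxicity, of 7 | Stopping rule | Phase IIA entry rule (safety part) |
|---|---|---|
| 0 to 2 | continue | safe |
| 3 | terminate | safe |
| 4 to 7 | terminate | not safe |

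**2. Do the differing terms remove the conflict?** No. Take three patients with one limiting toxicity each and no other treatment-related toxicity in the cohort. The count is three whether one counts patients, events or treatment-related toxicities of any kind. The PFS condition does not remove it either, because 4 of 7 progression free is compatible with three toxicities.

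**3. How often would a cohort land on three?** The plan states no operating characteristic for the Phase Ib rule, so there is no figure to reproduce. Let X be binomial with n = 7 (section 8.1) and true rate p. Then P(X = 3) = 35 p³(1 − p)⁴; at p = 0.20 this is 35 × 0.008 × 0.4096 = 0.115. For the four lymphoma cohorts, assuming a common rate and independence, P(at least one on exactly three) = 1 − (1 − P(X = 3))⁴. The rates are assumptions. The values 0.25 and 0.30 are borrowed from Phase IIA, where the event is broader.

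| True rate p | P(X = 3) | P(fail) if 3 stops, P(X ≥ 3) | P(fail) if 3 passes, P(X ≥ 4) | At least one of four cohorts on exactly 3 |
|---|---|---|---|---|
| 0.10 | 0.023 | 0.026 | 0.003 | 0.089 |
| 0.15 | 0.062 | 0.074 | 0.012 | 0.225 |
| 0.20 | 0.115 | 0.148 | 0.033 | 0.386 |
| 0.25 | 0.173 | 0.244 | 0.071 | 0.532 |
| 0.30 | 0.227 | 0.353 | 0.126 | 0.643 |

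**4. Precision of 3/7.** The exact (Clopper-Pearson) 95% interval runs from the 2.5% point of Beta(3, 5) to the 97.5% point of Beta(4, 4), which is 0.099 to 0.816.

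**5. What would Phase IIA do after a lenient go?** An exact recursion over the Table A boundary gives crossing probabilities of 0.772 at p = 0.25 and 0.897 at p = 0.30. Both match the high-boundary column of Table B. The same recursion at p = 3/7 gives a crossing probability of 0.996. The expected number of patients is 4.6 with monitoring after every patient, or 4.8 at the listed looks only. The first two looks can be checked by hand:
- No toxicity in the first 2 patients: (4/7)² = 0.327.
- Fewer than 2 in the next 3: 1 − [3(3/7)²(4/7) + (3/7)³] = 0.606.
- Not stopped by patient 5: 0.327 × 0.606 = 0.198, so about 80% of such cohorts stop by then.

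**The case against.** The strongest reply is that the documents nearly settle the matter. Termination is mandatory and appears four times, including in the dedicated stopping section, whereas expansion is only to be considered. Toxicity is monitored in real time, while the expansion test waits for 18-month PFS, so a cohort stopped at its third event would normally be closed before the entry rule applies. Section 8.1 also ties its three patients to events that lead to discontinuation, which leans towards stopping. This is a sensible inference and limits the seriousness of the point. But no passage states it, and three places define safe in a way that includes three.

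A second reply is that the probabilities overstate how often the go/no-go decision would change, because expansion also needs at least 4 of 7 progression free. This is correct. Assuming toxicity and PFS are independent, P(at least 4 of 7) is 0.29, 0.50 and 0.65 at an 18-month PFS of 40%, 50% and 57%. At a toxicity rate of 30%, the single-cohort figure of 0.227 falls to 0.07, 0.11 and 0.15, and the four-cohort figure falls from 64% to 24%, 38% and 47%. At a 10% toxicity rate the four-cohort figure falls from 9% to between 3% and 6%. The table above gives the chance of landing on three, not of a changed decision.

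Third, the rates are assumed, and the largest figures use rates taken from a broader event. That also stands, so the probabilities are illustrative.

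**Conclusion.** The contradiction is real and stands in current text: at exactly 3 of 7 the plan gives two opposite answers to its primary safety question. It does not depend on any assumed rate. Its likely frequency does: 2% to 23% per cohort over true rates of 10% to 30%, and lower as a changed decision once the PFS condition is applied. The choice of reading moves the chance of failing the safety gate from 15% to 3% at a true rate of 20%, and from 35% to 13% at 30%.

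The consequence is bounded by the probable precedence of the stopping rule, by the imprecision of 3/7, and by the Phase IIA boundary. It should be fixed, but it does not undermine the design.

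**What to change.** Reconcile the synopsis and sections 1.0, 8.0, 8.1 and 8.6:

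- Use one count: patients with at least one limiting toxicity as already defined, with the section 5.9 exceptions.
- Write the stopping rule as x or more patients, and define a safe cohort as one with fewer than x, so that no count falls under both.
- Replace the looser terms in the entry rule and in section 8.1 with the defined term.
- Record which rule was or will be applied to the Phase Ib cohorts.

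The sponsor chooses x; this review takes no position on its value. Stating the resulting probability of failing the gate at a few assumed rates would be useful but is optional. The cost is wording in an amendment plus a short note, with no change to sample size or data collection.
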